Disease worsening will continue to be monitored by Investigators through the 40-Week Treatment Period (ie, from Weeks 13 to 52). Subjects who either experience disease worsening in the 40-Week Treatment Period or complete all study procedures at Week 52 will have the option to enroll into the OLE study if they meet all eligibility criteria.

Subjects may be eligible to enroll in the OLE provided their ES is ≥ 2 and they meet one of the following entry criteria:

- RB subscore ≥ 2 at 2 timepoints at least 7 days and no more than 14 days apart
- RB + SF subscores ≥ 4 at 2 timepoints at least 7 days and no more than 14 days apart
- RB subscore ≥ 2 or RB + SF subscores ≥ 4 (in any order) at 2 timepoints at least 7 days and no more than 14 days apart

For subjects discontinuing prior to Week 52, an endoscopic evaluation is required to confirm eligibility for the OLE. An endoscopy should be performed upon the appearance of UC symptoms but no more than 14 days after the second timepoint for symptom criteria above. A proctosigmoidoscopy does not need to be repeated if performed within the last 4 weeks.

Subjects who do not participate in the OLE study will have 2-Week and 4-Week Follow-Up visits after their last treatment administration

End of 40-Week Double-Blind Treatment Period (Week 52)

At the end of the 40-Week Treatment Period (ie, Week 52) and following completion of all study procedures, subjects will have the option to enter into the OLE study (APD334-303) provided they meet all eligibility criteria.

Subjects who do not participate in the OLE study will have 2-Week and 4-Week Follow-Up visits after their last treatment administration

Number of subjects (planned):

Approximately 420 subjects are planned to be enrolled into this study.

Eligibility criteria:

Inclusion criteria:

Subjects must meet ALL of the following inclusion criteria to be eligible for enrollment into the study:

1. Men or women 16 to 80 years of age, inclusive, at the time of assent/consent. Enrollment of subjects < 18 years should be conducted only if acceptable according to local laws and regulations
2. Ability to provide written informed consent or assent (parent or legal guardian must provide consent for a subject < 18 years of age who has assented to participate in the study or as required per local regulations) and to be compliant with the schedule of protocol assessments

Disease-specific inclusion criteria:

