1.3. Benefit/Risk Assessment

Considering the significant unmet need for safe and effective, orally administered treatments for UC, etrasimod may potentially provide therapeutic benefit via S1P receptor modulation.

Adverse events that have been reported with S1P receptor modulators include bradycardia at the first dose or atrioventricular (AV) block, macular edema, hypertension, headache, cough, dyspnea, back pain, influenza, and diarrhea.

Safety and tolerability of etrasimod has been evaluated in Phase 1 studies with healthy adult subjects at single doses up to 5 mg and repeated doses up to 4 mg once daily. Repeated doses of 2 mg have been evaluated in Phase 2 studies of subjects with moderately to severely active UC (refer to the current edition of the IB). Etrasimod was found to be safe and well tolerated in these studies, with no clinically significant safety concerns with respect to vital signs, electrocardiograms (ECGs), pulmonary function tests (PFTs), ophthalmoscopy, or clinical laboratory tests. Etrasimod produced a dose-dependent sustained decrease in total lymphocyte count, which is expected given etrasimod's mechanism of action. Lymphocyte counts were within normal limits by 7 days after the last dose.

Detailed information regarding the known and expected benefits and risks and reasonably expected adverse events of etrasimod can be found in the IB.

Based on the mechanism of action of etrasimod and prior experience with other agents acting via a similar mechanism, monitoring for specific safety parameters are planned for this study, which include: auscultation of the lungs as part of the physical exam; PFT, exclusion of subjects with macular edema or retinopathy, with assessment of optical coherence tomography (OCT) occurring throughout the study; and exclusion of subjects with certain cardiac risks, with assessment of vital signs in the period following dosing.

- Auscultation of lungs will be conducted as part of the physical examination.
- Prospective subjects with a history of macular edema or retinopathy will be excluded from the study. All randomized subjects will be assessed by OCT at study entry, periodically throughout the treatment period, and as clinically indicated any time during the study.

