Subjects must complete Week 12 to be eligible for the OLE. Subjects who do not meet disease worsening criteria, including those demonstrating clinical response/remission at Week 12 will continue into the 40-Week Treatment Period and continue their double-blind treatment. Disease worsening will continue to be monitored by Investigators through the 40-Week Treatment Period (ie, from Weeks 13 to 52). Subjects who either experience disease worsening in the 40-Week Treatment Period or complete all study procedures at Week 52 will have the option to enroll into the OLE study if they meet all eligibility criteria.

Subjects who discontinue from the study and do not participate in the OLE study will have 2-Week and 4-Week Follow-Up visits after the last on-treatment visit/Early Termination visit (Table 7).

Figure 1: Study Design

JAK, Janus kinase; UC, ulcerative colitis

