3.2. Rationale for Study Design

This study is designed to evaluate the efficacy and safety of etrasimod in subjects with moderately to severely active UC. Subjects may continue existing nonbiologic therapy for UC

(eg, 5-ASA, corticosteroids) per the concomitant medication and dose stabilization criteria. As preexisting background therapy is allowed, a placebo comparator is justified.

The duration of study treatment is up to 52 weeks, which includes 12- and 40-Week Treatment Periods. The 40-Week Treatment Period is expected to provide adequate time for separation of efficacy effects between etrasimod and placebo. The 2-Week and 4-Week Follow-Up visits will provide off-treatment safety information.

The etrasimod dose of 2 mg once daily is based on findings of previous Phase 1 and Phase 2 studies, and in particular data from the Phase 2 APD334-003 placebo-controlled study. In the APD334-003 study, subjects received etrasimod 1 mg, etrasimod 2 mg, or placebo. Subjects in the etrasimod 2 mg group experienced a statistically significant improvement in the primary endpoint, the mean difference from placebo at Week 12 in the adapted Mayo score (least squares mean [standard error] difference: -0.99 [0.42]; $p = 0.0091$) compared with placebo. The etrasimod 2 mg group also experienced significant improvement in all secondary endpoints compared with the placebo group at Week 12 including, improvement in the total Mayo Score (estimated least squares mean [standard error] difference from placebo: -1.27 [0.55]; $p = 0.0100$), and higher percentage of subjects with endoscopic improvement (41.8%, difference from placebo: 24.4%, $p = 0.003$).

Treatment-emergent adverse events (TEAEs) in the 1 mg, 2 mg, and placebo groups were reported for 59.6%, 56.0%, and 50.0% of subjects, respectively; treatment-related TEAEs were reported for 7.7%, 10.0%, and 5.6% of subjects, respectively; serious adverse events (SAEs) were reported for 5.8%, 0%, and 11.1% of subjects, respectively; and TEAEs leading to discontinuation of study treatment were reported for 5.8%, 8.0%, and 0% of subjects, respectively. No subjects died during the study. Overall, the 2 mg dose demonstrated a favorable safety profile and was chosen as the dose for the current Phase 3 program.

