Subjects who discontinue treatment prematurely, regardless of the reason, should be instructed to return for an Early Termination (ET) visit within 7 days of the last administration of study treatment (Table 7 and Table 8) and before initiation of any new treatments to complete all of the ET assessments. If a subject discontinues due to pregnancy, they are not required to complete the endoscopy. If the ET visit is within 4 weeks of the last sigmoidoscopy and biopsy, these procedures do not need to be repeated.

If the ET visit is ≥ 2 weeks of the last administration of study treatment, the 2-Week Follow-Up visit is not required; however, the 4-Week Follow-Up visit should be scheduled and completed. If the ET visit is ≥ 4 weeks of the last administration of study treatment, the 4-Week Follow-Up visit is not required unless the absolute lymphocyte count (ALC) is not within normal limits.

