9.5. Follow-Up Period

For subjects not participating in the OLE study, a follow-up visit, will be performed at 2 and 4 weeks after the last administration of study treatment as indicated in the Schedules of Assessments (Table 7 and Table 8).

If the ET or Study Completion visit is ≥ 2 weeks after the last administration of study treatment, the 2-Week Follow-Up visit is not required; however, the 4-Week Follow-Up visit should be

scheduled and completed. If the ET or Study Completion visit is ≥ 4 weeks after the last administration of study treatment, the 4-Week Follow-Up visit is not required.

If the absolute peripheral lymphocyte count is not within normal limits at the 4-Week Follow-Up visit, subjects should return for CBC with differential according to local standard of care (captured as subsequent Follow-Up visit or unscheduled visit).

All adverse events should be recorded for 30 days after last administration of study treatment (Section 9.10.8.2.2).

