| Ophthalmoscopy with OCT | X ^r | | | | | X ^r | X ^r | |
| Urine drug screen ^s | X | | | | | | | |
| Pregnancy test ^t | X | X | | X | X | X | | X |
| Genomic DNA (optional) | | X | | | | | | |
| CBC with differential and platelets | X | X | X | X | X | X | X | X |
| TBNK | X | X | X | X | X | X | X | X |
| Laboratory tests including hs-CRP ^u | X | X | X | X | X | X | X | |
| Stool sample/fecal calprotectin ^v | X | | X | X | X | X | | |
| Stool sample for microbiome | X | | | | | X | | |
| Flexible proctosigmoidoscopy/colonoscopy and biopsy ^w | X | | | | | X | | |
| PK assessments ^x | | X | X | X | X | X | X ^x | X ^x |
| Biomarkers blood sample ^y | | X | | | | X | | |
| Concomitant medications and procedures ^z | | X | X | X | X | X | X | X |
| Drug dispensation/ accountability | | X | X | X | X | X ^{aa} | | |
| Study treatment administration ^{bb} | | X – Once daily | | | | | | |

- ^a All visits beyond W0/D1 may be virtual/hybrid visits (Section 9.6). Subjects discontinuing prior to Week 12/Day 85 should have an Early Termination (ET) visit within 7 days of the last study treatment administration and before initiation of any new treatments. For subjects who complete Week 12, the Week 12 visit will be used to begin assessing eligibility for the APD334-303 OLE study.
- ^b For subjects not participating in the APD334-303 OLE study, a follow-up visit will be performed at 2 and 4 weeks after the last administration of study treatment. If the ET or Study Completion visit is ≥ 2 weeks after the last dose of study treatment, the 2-Week Follow-Up visit is not required; however, the 4-Week Follow-Up visit should be scheduled and completed. If the ET or Study Completion visit is ≥ 4 weeks after the last administration of study treatment, the 4-Week Follow-Up visit is not required. If the absolute peripheral lymphocyte count is not within normal limits at the 4-Week Follow-Up visit, subjects should return for CBC with differential according to local standard of care (captured as subsequent Follow-Up visit or unscheduled visit).
- ^c Medical history, including prior and ongoing medication use, will be collected during screening and should be updated for any new conditions or medications as needed prior to dosing at the D1 visit (Section 9.3.5).
- ^d A chest X-ray taken within the previous 6 months from the Screening Visit may also be used.

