^a All visits beyond W0/D1 may be virtual/hybrid visits (Section 9.6). Subjects discontinuing treatment prior to Week 52/Day 365 should have an Early Termination (ET) visit within 7 days of the last study treatment administration and before initiation of any new treatments. If a subject discontinues at or before Week 16, a sigmoidoscopy and biopsy are not required. For subjects with worsening disease or who complete Week 52 and wish to enter the APD334-303 OLE study, the Week 52/Early Termination visit will be used to assess eligibility for the OLE study.

^b For subjects discontinuing study treatment, 2-Week and 4-Week Follow-Up visits should be scheduled 2 weeks and 4 weeks after the Week 52/Early Termination visit and the indicated assessments performed; however, if the ET or Week 52 visit is ≥ 2 weeks after the last dose of study treatment, the 2-Week Follow-Up visit is not required; however, the 4-Week Follow-Up visit should be scheduled and completed. If the ET or Week 52 visit is ≥ 4 weeks after the last dose of study treatment, the 4-Week Follow-Up visit is not required. If the absolute peripheral lymphocyte count is not within normal limits at the 4-Week Follow-Up visit, subjects should return for CBC with differential according to local standard of care (captured as subsequent Follow-Up visit or unscheduled visit).

^c The Week 52 MMS will be calculated using the Week 52 proctosigmoidoscopy and SF and RB scores completed by the subject 7 days prior to the visit using the 3 most recent consecutive days prior to the actual day of the study visit excluding the day of bowel preparation.

^d Stool frequency and RB subject-reported outcomes recorded daily using eDiary. The RB and SF subscores will be calculated as indicated in Section 9.4.2.

^e Safety vital signs will include resting heart rate and systolic and diastolic BP with subjects in the sitting position taken before dosing. The Day 1 safety monitoring (Section 9.4.2.1) should be repeated if a subject has had a dose interruption ≥ 2 consecutive days within the first week of treatment or ≥ 7 consecutive days after the first week of treatment.

^f At Week 52, a complete physical examination (including assessments of the skin, head, eyes, ears, nose, throat, neck, thyroid, lungs, heart, abdomen, back, lymph nodes, extremities, and body weight) should be performed. All other visits should have a focused (complaints, signs, and symptoms) physical examination.

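### Table 8 footnote b times the 2-Week and 4-Week Follow-Up visits from the Week 52/Early Termination visit, while Section 9.5 times them from the last dose

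*Protocol*

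**What the plan says.** The protocol gives two starting points for the same two visits.

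- **Table 8 footnote b** (40-Week Treatment Period): "2-Week and 4-Week Follow-Up visits should be scheduled 2 weeks and 4 weeks after the Week 52/Early Termination visit". The same footnote measures its rules for dropping a follow-up visit from the last dose, so it uses both starting points.
- **Section 9.5**, for subjects not entering the OLE: "2 and 4 weeks after the last administration of study treatment as indicated in the Schedules of Assessments (Table 7 and Table 8"). It names both tables, so it covers the Table 8 subjects.
- **Table 7 footnote b** (Screening and 12-Week Treatment Period): "a follow-up visit will be performed at 2 and 4 weeks after the last administration of study treatment".
- **Synopsis**: "Subjects who do not participate in the OLE study will have 2-Week and 4-Week Follow-Up visits after their last treatment administration".

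Two other places are loosely worded. Protocol Section 3.1 has "Follow-Up visits after the last on-treatment visit/Early Termination visit (Table 7"), which leans towards the ET visit but gives no interval and points to the table whose footnote uses the last dose. SAP Section 3.1 joins the last administration and the ET visit with a slash.

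On the ET visit itself, Section 5.1 says that subjects who stop early "should be instructed to return for an Early Termination (ET) visit within 7 days of the last administration of study treatment". Section 3.2 gives the purpose of the follow-up visits: "The 2-Week and 4-Week Follow-Up visits will provide off-treatment safety information".

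**The concern.** The last dose and the ET visit need not fall on the same day. When they differ, a site following Table 8 and a site following Section 9.5 will book the same visit for different days, and a visit that is in window under one rule can be out of window under the other. In the analysis, a visit label such as 2-Week Follow-Up would mean one time off drug for subjects who stop under Table 7 and another for those who stop under Table 8.

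The SAP does not correct for this. Section 6.4 leaves the follow-up visits out of the analysis windows and summarizes them as labelled. Section 18.3.1 reports lymphocyte recovery by these labels, both as return to the normal range and as the share at 80% or more of Baseline. Section 20 summarizes PK by nominal timepoint. A visit meant to describe what happens off treatment is best timed from the end of treatment.

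**Working it through.** The plan has no figure to reproduce. The check compares the text and counts days.

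**Inputs**
- Gap d from last dose to ET visit: 0 to 7 days for an on-time visit (Section 5.1; Table 8 footnote a).
- Visit window: ±3 days for both follow-up visits (column headings of Tables 7 and 8).
- Section 9.5 targets: days 14 and 28 after the last dose.
- Table 8 footnote b targets: days 14 + d and 28 + d after the last dose.

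**Windows, in days after the last dose**
- Section 9.5: 14 ± 3 = days 11–17, and 28 ± 3 = days 25–31, whatever d is.
- Table 8: (14 + d) ± 3 and (28 + d) ± 3.
- Days shared by two 7-day windows shifted by d: 7 − d.

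| d | Table 8, 2-Week | Table 8, 4-Week | Days shared with Section 9.5 |
|---|---|---|---|
| 0 | 11–17 | 25–31 | 7 |
| 1 | 12–18 | 26–32 | 6 |
| 2 | 13–19 | 27–33 | 5 |
| 3 | 14–20 | 28–34 | 4 |
| 4 | 15–21 | 29–35 | 3 |
| 5 | 16–22 | 30–36 | 2 |
| 6 | 17–23 | 31–37 | 1 |
| 7 | 18–24 | 32–38 | 0 |

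At d = 7 the targets are days 21 and 35 under Table 8, against days 14 and 28 under Section 9.5. No day satisfies both rules. For a Week 52 completer dosed at the visit, d = 0 and the rules coincide.

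**Likely effect on the lymphocyte summaries.** Section 1.3 reports from earlier studies: "Lymphocyte counts were within normal limits by 7 days after the last dose". The earliest follow-up visit under either rule is day 11, which is 11 − 7 = 4 days later. The normal-range summary should therefore change little. That statement does not cover the 80%-of-Baseline summary.

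**The case against.** The strongest reply is that this is a drafting slip that a site can resolve. Section 9.1 describes the schedules as a summary of procedures and timing, the body text in Section 9.5 states the last-dose rule, and footnote b's own waivers run from the last dose. The synopsis is also not a firm rule, because a visit timed from the ET visit still comes after the last administration. Table 7 governs a different period. On this view the direct contradiction is one pair of sentences. Moreover, for d = 0 to 6 at least one day satisfies both windows, and a ±3-day window already allows a 7-day spread under a single label.

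Much of this is fair. Section 9.5 against Table 8 footnote b is the pair that carries the point, and the synopsis and Table 7 support it. Strict incompatibility arises only at d = 7. But the target days differ at every d above 0, and Section 9.1 also makes adherence to the schedules a requirement, so a site that follows footnote b literally is doing as told.

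The safeguards also limit the harm:
- A subject whose lymphocyte count is not normal at the 4-Week visit returns for further counts, and SAP Section 18.3.1 has a Last Follow-Up row.
- The SAP's listings carry study day, and the last-dose date is recorded, so days off drug can be derived.
- The PK listing already shows time since last dose.
- Adverse events are recorded for 30 days from the last dose regardless of visit dates.

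These let a reader recover the timing for each subject. They do not realign the summaries by visit label.

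**Conclusion.** The inconsistency is real and rests on current text alone. For an on-time ET visit it moves both follow-up visits by 0 to 7 days, and the two windows do not overlap when the gap is 7 days. Section 3.2's purpose for the visits favours the last-dose anchor.

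Severity is minor. Efficacy, adverse event capture and Week 52 completers dosed up to the visit are essentially unaffected. What remains is descriptive: follow-up lymphocytes and nominal-time PK for early stoppers in the 40-Week period who do not enter the OLE. The documents give neither the number of such subjects nor the distribution of d, so the change in the summaries cannot be sized; it is probably small. Confidence is high for the wording conflict and does not extend to any effect on results. The day counts assume ET visits on schedule; a later ET visit would widen the shift.

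**What to change.** In Table 8 footnote b, replace the Week 52/ET visit anchor with the one in Section 9.5: 2 and 4 weeks from the last administration of study treatment. Use the same anchor in protocol Section 3.1 and SAP Section 3.1 for consistency; the SAP edit changes no analysis. Leave the waivers in footnote b as they are, since they already run from the last dose.

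Optionally, add days since last dose to the follow-up lymphocyte listing, as SAP Section 20 already does for PK. This would also show actual time off drug for visits already done.

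The cost is one line in the footnote and a few matching words elsewhere, with no extra visit, sample or analysis. The optional column uses dosing dates already collected.

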APPENDIX 2: TUBERCULOSIS SCREENING

All subjects must undergo screening for a history of TB infection and testing for latent/active TB infection. Their medical history review must include specific questions about a history of TB or known occupational or other personal exposure to individuals with active TB. Subjects should be asked about past testing for TB, including chest radiograph results and results of interferon-gamma release assay (IGRA, eg, QuantiFERON-TB Gold In-Tube, T-SPOT TB) or response to tuberculin skin test (TST) and history of Bacillus Calmette-Guérin vaccination.

- a. Subjects without a history of latent or active TB who have a negative IGRA or TST result at screening are eligible to enroll in the study.
- b. A TB questionnaire will be completed for all subjects (refer to questionnaire below) during the Screening period.
- c. For subjects residing in countries with a high burden of TB or MDR TB as identified by WHO, the TB screening questionnaire will be completed at every study visit (per protocol schedules of assessments). For subjects who are receiving TB prophylaxis treatment the TB questionnaire will be completed at every study visit (until TB prophylaxis treatment course is completed). This questionnaire will monitor for any emergent symptoms of active TB and compliance with any TB prophylaxis treatment.
 - For a complete list of TB high burden and MDR TB high burden countries during the period 2016 to 2020, visit:
 - <http://www.stoptb.org/countries/tbdata.asp>
 - https://www.who.int/tb/publications/global_report/high_tb_burdencountrylists/2016-2020.pdf?ua=1
- d. The IGRA or TST is NOT required at screening (or annually) for subjects with a history of active/latent TB infection.
 - Subjects with past or current history of active TB, regardless of treatment history, are excluded from enrollment.
 - Subjects with a history of latent TB infection diagnosed prior to screening must have documentation of treatment with at least four weeks of an acceptable TB prophylaxis treatment regimen to qualify for enrollment. It is the responsibility of the investigator to verify the adequacy of previous TB treatment and provide appropriate documentation (Direct Observation Therapy report where available).
- e. Acceptable TB prophylaxis treatment regimens for latent TB is defined according to local country guidelines. If no local country guidelines for the treatment of latent TB exist, WHO guidelines must be followed.
- f. Subjects with a newly identified positive IGRA (one retest is allowed with approval from the Medical Monitor per Section 9.3.1) or TST result at Screening must be considered a Screen Failure, however they are eligible for rescreening once they undergo an evaluation to rule out active TB (chest x-ray to rule out pulmonary TB) and initiate an acceptable TB prophylaxis treatment regimen for latent TB at least 4 weeks prior to rescreening (with a plan to complete the TB treatment course during study participation) before they can be considered for enrollment. For subjects

diagnosed with latent TB infection and reside in countries with high burden of TB or MDR TB: A chest CT scan should be performed to rule out current/past pulmonary TB in the event the chest X-ray is equivocal.

- g. An assessment of adequacy of the TB prophylaxis treatment regimen and duration of treatment must be performed by an infectious disease consultant or physician TB expert.
- h. IGRA and TST interpretation
 - Subjects will be considered to have a negative diagnostic test for TB if at least one of the following circumstances applies:
 - Negative QuantiFERON-TB Gold test.
 - Combination of a negative QuantiFERON-TB Gold test and negative purified protein derivative (PPD) TST (in countries where IGRA is not considered a validated test).
 - A combination of two indeterminate QuantiFERON-TB Gold tests and a negative PPD TST (in countries where IGRA is not considered a validated test). An indeterminate IGRA test result should be repeated. In the event that the second IGRA test result is also indeterminate, the subject may be enrolled without treatment for latent TB if his/her chest radiograph shows no abnormality suggestive of TB (active or old, inactive TB) and the subject has no additional risk factors for TB as determined by a physician TB expert physician.
 - If the IGRA is not considered a validated test or is not registered for use in the subject's country, a negative TST result is required to rule out latent TB infection.
 - A positive TST reaction is ≥ 10 mm of induration, or ≥ 5 mm of induration for subjects receiving equivalent of prednisone > 15 mg/day for any medical conditions and subjects residing in countries identified by WHO as a high TB burden country or high MDR TB burden country.
- i. Resources
 - For the WHO guidelines for the treatment of latent TB visit:
https://apps.who.int/iris/bitstream/handle/10665/44165/9789241547833_eng.pdf;jsessionid=115F807C3008D688F75118AF16EA53F0?sequence=1

Tuberculosis Screening Questionnaire

Etrasimod Program
Tuberculosis Screening Questionnaire
Created by Arena Pharmaceuticals, Inc.
Version 1.0, 17Jan2020

Site #: _____
Subject #: _____

Tuberculosis Screening Questionnaire Source Document Worksheet

Instructions:

1. This source document worksheet should be completed by the PI or delegated site staff.
2. This source document worksheet should **NOT** be given to the subject for completion.
3. Please complete for **ALL** subjects during the Screening visit.
4. Please complete at every study visits for subjects who are receiving TB prophylaxis treatment (until the TB prophylaxis treatment course is completed) and at designated post-baseline study visits (per protocol schedule of assessments) for subjects who reside in countries with a high burden of TB or multi-drug resistant (MDR) TB as identified by WHO. The current WHO TB high burden country (HBC) and MDR TB HBC lists can be found at the following URL:
<http://www.stoptb.org/countries/tbdata.asp>.
5. Enter all applicable information on the corresponding eCRF.

Was the Tuberculosis Screening questionnaire completed? Yes/No

If yes, please enter completion date (DD/MM/YYYY): _____

If no, specify reason:

Date of completion of TB Screening Questionnaire, if applicable: _____

Study Visit Number: _____

Section 1: Questions to ask the subject

*Time frame: in the past year or since your last study visit.

| | |
|------------------------------------------------------------------|----------|
| 1. Have you experienced any of the following symptoms ?* | |
| a) A productive cough (coughing up phlegm) for more than 3 weeks | Yes / No |
| b) Hemoptysis (coughing up blood) | Yes / No |
| c) Unexplained weight loss | Yes / No |
| d) Fever, chills, or night sweats for no known reason | Yes / No |
| e) Persistent shortness of breath (difficulty breathing) | Yes / No |
| f) Unexplained fatigue | Yes / No |
| g) Chest pain | Yes / No |

Page 1 of 3

Etrasimod Program
Tuberculosis Screening Questionnaire
Created by Arena Pharmaceuticals, Inc.
Version 1.0, 17Jan2020

Site #: _____
Subject #: _____

| | |
|----------------------------------------------------------------------------------------------------------------------------------------------------------------------------------------------------------------------------------------------------------------------------------------------------------------------------------------------------------------------------------------------------------------------------------------------------------------------------------------------------------------------------------------------------------------------------------------------------------------------------------------------------------------------------------------------------------------------------------------------------------------------------------------------------------------------------------------------------------------------------------------------------------------------------------------------------------------------------------------------------------------------------------------------------------------------------------------------------------------------------------------------------------------------------------------|-----------------------------------------------------------------|
| 2. Have you had contact with anyone with active tuberculosis disease ? | Yes / No |
| 3. Have you been diagnosed with latent TB infection? | Yes / No |
| 
a) If yes, list medication(s) used to treat latent TB infection and treatment dates (please ensure listed on Concomitant Medication Source Log and eCRF, as applicable).
 
Medication #1: _____ Start date of Medication #1: _____ Expected stop date of Medication #1: _____ Have you missed taking any doses of Medication #1? _____ Dates of Missed Doses: _____ # of Missed Doses: _____
 
Medication #2: _____ Start date of Medication #2: _____ Expected stop date of Medication #2: _____ Have you missed taking any doses of Medication #2? _____ Dates of Missed Doses: _____ # of Missed Doses: _____
 
Medication #3: _____ Start date of Medication #3: _____ Expected stop date of Medication #3: _____ Have you missed taking any doses of Medication #3? _____ Dates of Missed Doses: _____ # of Missed Doses: _____
 
Medication #4: _____ Start date of Medication #4: _____ Expected stop date of Medication #: _____ Have you missed taking any doses of Medication #4? _____ Dates of Missed Doses: _____ # of Missed Doses: _____
 | 
Yes / No
 
Yes / No
 
Yes / No
 
Yes / No
 |

Please provide details to any question answered "Yes."

Completed by (signature)

Date

Etrasimod Program
Tuberculosis Screening Questionnaire
Created by Arena Pharmaceuticals, Inc.
Version 1.0, 17Jan2020

Site #: _____
Subject #: _____

Section 2: To be completed by the investigator

I. The participant is on concomitant medication(s) with immunosuppressive effects: Yes / No
If yes, specify medication(s) (name, dosage):

Medication #1:

Medication #2:

Medication #3:

Medication #4:

II. TB QuantiFERON or Tuberculin Skin Test result: _____ Date: _____

Chest x-ray/computer tomography (CT) scan done to rule out pulmonary TB? Yes / No

If yes, date of chest x-ray or CT scan: _____

Any evidence of active pulmonary TB disease on chest x-ray or CT scan? Yes / No

Other assessment completed? Yes / No

If yes, specify assessment: _____

If yes, date of other assessment: _____

Any evidence of active TB disease on assessment? Yes / No

III. Upon review of the responses and discussion with the participant, I recommend the following:

___ Perform screening test for latent TB infection

___ Perform additional assessments to rule out active TB disease

___ Refer to physician TB expert for evaluation and treatment

___ Follow up at the next TB-designated study visit and repeat TB screening questionnaire

Investigator (signature)

Date

